1. To assess ability of eltrombopag to induce sustained remission by month 12 in ITP patients who relapsed or failed to respond to first-line steroid treatment.	1. Proportion of patients with sustained remission (R) by month 12 where sustained remission is defined as: 
reach platelet count $\geq 100 \times 10^9/L$ (complete response [CR]) and then maintain platelet counts around $100 \times 10^9/L$ for 2 months (no counts below $70 \times 10^9/L$) AND thentaper off the drug until treatment discontinuation (see Section 9.1) while,maintain platelet count $\geq 30 \times 10^9/L$ in the absence of bleeding (no bleeding AEs) or use of any rescue therapy (see Section 6.2.3) until month 12.
Secondary Objective(s)	Endpoints for secondary objective(s)
1. To assess the duration of sustained remission after treatment discontinuation by month 12 and by month 24	1a. Median duration of sustained remission (weeks) counted from last dose of eltrombopag to month 12 for patients with sustained remission (R) 1b. Estimated median duration of sustained remission (weeks) by month 24 for patients who are in sustained remission (R) at month 12 and enter 12 months follow-up period using Kaplan-Meier method 1c. Estimated median duration of sustained remission (weeks) by month 24 for all patients using Kaplan-Meier method.
2. To assess the proportion of patients maintaining a sustained remission after treatment discontinuation until month 24.	2. Proportion of sustained remission (R) patients at months 15, 18, 21, and 24.
3. To assess the ability of eltrombopag to induce early response by month 1	3. Number (%) of patients with platelet count $\geq 50 \times 10^9/L$ at least once by month 1 (first month) without bleeding and no rescue therapy
4. To assess the ability of eltrombopag to induce a recovery response, in case of loss of response during or after tapering of eltrombopag until month 24	4. Number (%) of patients with at least one platelet count $\geq 30 \times 10^9/L$ after eltrombopag is re-introduced, in case of loss of response ($< 30 \times 10^9/L$ and/or bleeding event) without bleeding and no rescue therapy by month 12 and 24
5. To assess the platelet count from baseline and every 3 months until month 24	5. Absolute and relative change in platelet count from baseline to 3, 6, 9, 12, 15, 18, 21, and 24 months and end of treatment

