12.5.1 Efficacy endpoint(s)

1. To assess the **duration of sustained remission** after treatment discontinuation

1a) Summary statistics for the duration of sustained remission (weeks) counted from last dose of eltrombopag to month 12 for patients with sustained remission (R) will be provided.

1b) Kaplan-Maier analyses for the duration of sustained remission (weeks) counted from last dose of eltrombopag to relapse for patients with sustained remission (R) at month 12 and who enter 12 months follow-up period. The patients who do not relapse/die by month 24 will be censored.

1c) Kaplan-Maier analyses for the duration of sustained remission (weeks) counted from last dose of eltrombopag to relapse for all patients. The patients who do not relapse/die by month 24 will be right-censored. The duration will be considered as 0 for patients who do not manage to taper off eltrombopag per protocol i.e. do not reach sustained remission.

2. To assess the proportion if patients maintaining a sustained remission after treatment discontinuation until month 24.

Number (%) of patients who are in sustained remission at months 15, 18, 21, and 24 will be provided.

3. To assess the ability of eltrombopag to induce **early response by month 1**

Number (%) of patients who reach platelet count $\geq 50 \times 10^9/L$ at least once within the first month (month 1) without bleeding events and no rescue therapy will be provided.

4. To assess the ability of eltrombopag to induce a **recovery response**, in case of loss of response during or after tapering of eltrombopag

Number (%) of patients with at least one platelet count $\geq 30 \times 10^9/L$ after eltrombopag is re-introduced, in case of loss of response ($< 30 \times 10^9/L$ and/or bleeding event) without bleeding events and no rescue therapy will be provided.

5. To assess the **platelet count** from baseline to 3, 6, 9, 12, 15, 18, 21, 24 months

Absolute and relative change in platelet count from baseline to 3, 6, 9, 12, 15, 18, 21, 24 months and end of treatment will be provided. Box plots for absolute and/or relative change in platelet counts from baseline to different time points will also be provided.

6. To assess the ability of eltrombopag to **maintain platelet count $\geq 30 \times 10^9/L$** within 12 months and every 3 months until month 24

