1.2 Study objectives and endpoints

Table 1-1 Objectives and endpoints

Objective(s)	Endpoint(s)
Primary Objective(s)	Endpoints for primary objective(s)
Secondary Objective(s)	Endpoints for secondary objective(s)
1. To assess ability of eltrombopag to induce sustained response off treatment by month 12 in ITP patients who relapsed or failed to respond to first-line steroid treatment.	1. Proportion of patients with sustained response off treatment by month 12 where sustained response off treatment is defined as: 
 reach platelet count $\geq 100 \times 10^9/L$ (complete response [CR]) and then maintain platelet counts around $100 \times 10^9/L$ for 2 months (no counts below $70 \times 10^9/L$) AND then taper off the drug until treatment discontinuation (see Section 9.1 of the study protocol) while, maintain platelet count $\geq 30 \times 10^9/L$ in the absence of bleeding (no bleeding AEs) or use of any rescue therapy (see Section 6.2.3 of the study protocol) until month 12.
2. To assess the duration of sustained response off treatment after treatment discontinuation by month 12 and month 24	1a. Median duration of sustained response off treatment (weeks) counted from last dose of eltrombopag to month 12 for patients with sustained response off treatment 1b. Estimated median duration of sustained response off treatment (weeks) by month 24 for patients who are in sustained response off treatment at month 12 and enter 12 months follow-up period using Kaplan-Meier method 1c. Estimated median duration of sustained response off treatment (weeks) by month 24 for all patients using Kaplan-Meier method.
3. To assess the proportion of patients maintaining a sustained response off treatment after treatment discontinuation until month 24.	2. Proportion of sustained response off treatment patients at months 15, 18, 21, and 24.
4. To assess the ability of eltrombopag to induce early response by month 1	3. Number (%) of patients with platelet count $\geq 50 \times 10^9/L$ at least once by month 1 (first month) without bleeding and no rescue therapy
5. To assess the platelet count from baseline and every 3 months until month 24	4. Number (%) of patients with at least one platelet count $\geq 30 \times 10^9/L$ after eltrombopag is re-introduced, in case of loss of response ($< 30 \times 10^9/L$ and/or bleeding event) without bleeding and no rescue therapy by month 12 and 24

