2.7.1 Secondary endpoints

2.7.2 Efficacy endpoint(s)

1. To assess the **duration of sustained response off treatment** after treatment discontinuation
 - 1a) Summary statistics for the duration of sustained response off treatment (weeks) counted from last dose of eltrombopag to month 12 for patients with sustained response off treatment

(SRoT_M12 patients) will be provided. Mean, SD, median, maximum, minimum, 25th percentile and 75th percentile will be provided.

1b) Kaplan-Maier analysis and corresponding plot for the duration of sustained response off treatment for all patients meeting the primary endpoint (SRoT_M12 patients) (weeks) will be provided and is counted from last dose of eltrombopag to relapse. The SRoT_M12 patients who do not relapse/ restart eltrombopag treatment until month 24 will be censored.

- Event: relapse after achieving SRoT_M12 (platelets <30 Gi/L, bleeding event, rescue therapy/platelet transfusion, or restarted eltrombopag treatment)
- Censoring rules: Patients with SRoT_M12 who enter follow-up and do not relapse by cut-off date/Month 24 will be censored at the earliest of discontinuation date/death date/M24 platelet assessment date/cutoff date. SRoT_M12 patients who did not enter or do not yet have platelet assessments in follow-up phase are censored at their M12 platelet assessment date.

1c) Kaplan-Maier analysis and corresponding plot for the duration of sustained response off treatment for all patients who achieved Step 3 (S3 patients) (weeks) will be provided and is counted from their last dose of eltrombopag on or before this last S3 to relapse.

The S3 patients who do not relapse/ restart eltrombopag treatment until month 24 will be censored.

The event and censoring rules are as in 1b) above.

It is noted that the SRoT_M12 patients are a subset of patients in the group of patients who achieved Step 3 (S3 patients).

Duration of SRoT (weeks) for the tapered patients who achieved step 3 will be summarized by SRoT_M12 status.

2. To assess the proportion of patients maintaining a sustained response off treatment after treatment discontinuation until month 24. Number (%) of patients who are in sustained response off treatment at months 15, 18, 21, and 24 will be provided.
3. To assess the ability of eltrombopag to induce **early response by month 1**

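### SAP 2.7.2 item 1c estimates response duration only in Step 3 achievers, although the protocol and SAP Table 1-1 plan it for all patients; the protocol's zero-duration rule is dropped and SAP section 4 names neither change

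*SAP*

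**What the plan says.** **All patients.** Protocol Table 2-1 gives the endpoint as "1c. Estimated median duration of sustained remission (weeks) by month 24 for all patients using Kaplan-Meier method". SAP Table 1-1 repeats it: "1c. Estimated median duration of sustained response off treatment (weeks) by month 24 for all patients using Kaplan-Meier method". SAP 2.7 names the full analysis set (FAS) for all efficacy analyses, and SAP 2.2 defines that set as everyone who took at least one dose.

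**Protocol rule for patients who do not taper off.** Protocol 12.5.1, item 1c, runs the clock from last dose to relapse in all patients. Duration is "considered as 0 for patients who do not manage to taper off eltrombopag per protocol i.e. do not reach sustained remission". On censoring it says: "The patients who do not relapse/die by month 24 will be right-censored".

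**Step 3 patients only.** SAP 2.7.2, item 1c, plans the analysis "for all patients who achieved Step 3 (S3 patients) (weeks) will be provided and is counted from their last dose of eltrombopag", using the last dose on or before the last time Step 3 was met. Step 3 (SAP 2.5.2) means tapered to discontinuation with platelets of at least 30, no bleeding AE and no rescue. The item adds "The S3 patients who do not relapse/ restart eltrombopag treatment until month 24 will be censored" and "The event and censoring rules are as in 1b) above". In 1b the event is headed "Event: relapse after achieving SRoT_M12". Both dated censoring rules in 1b refer only to month-12 responders (SRoT_M12), and one of them censors at death.

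**Disclosure.** For 2.7.2, SAP section 4 records only that the description was updated and that event and censoring rules were added. The revision history dates an update of 2.7.2 to 07-Sep-2022, before the final database lock. The SAP introduction says the primary CSR was already final at that addendum.

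**The concern.** Items 1a and 1b are confined to month-12 responders. Item 1c was the one duration analysis meant to cover every treated patient, and the zero rule is what makes that possible: someone who never comes off the drug contributes no treatment-free time but stays in the denominator.

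Restricting 1c to Step 3 conditions on a success that happens after baseline. It then answers how long response lasts in those who managed to stop, not how much treatment-free response a patient starting eltrombopag can expect. The shift has a known direction. A reader who takes the endpoint from either objectives table and the result from the 2.7.2 output would compare two different quantities, and section 4 would not alert them.

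**Working it through.** **Inputs.** The documents give no figure for 1c and no share reaching Step 3. From SAP 3.1.1 and 3.1.2 come the final sample size (105) and the design rate (25%). As a check on that source, rejecting at 23 or more of 105 gives an exact one-sided alpha of 0.0373 and power of 0.7995, against the stated 0.037 and 0.800. Those two figures do not bear on 1c.

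**Relation between the two curves.** Read the protocol's zero rule as applying to patients who do not reach Step 3. They are then events at time 0, with all 105 at risk. Put p = (number at Step 3)/105. On the same clock:

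S_all(t) = p × S_S3(t)

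This holds for the Kaplan-Meier estimate too, because events at time 0 only multiply the later curve by p. As p cannot exceed 1, the Step 3 median cannot be the shorter one. The all-patient median is the time at which S_S3(t) = 0.5/p.

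**When the median is 0.** 52/105 = 0.495, so the curve starts at or below one half and the median is 0. 53/105 = 0.505, so it is above 0.

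**When more patients reach Step 3** (assumed shares, any relapse distribution):

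| At Step 3 | p | 0.5/p | Step 3 patients relapsed at the all-patient median |
|---|---|---|---|
| 63 | 0.600 | 0.833 | 16.7% |
| 74 | 0.705 | 0.709 | 29.1% |
| 84 | 0.800 | 0.625 | 37.5% |

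The Step 3 median is by definition the time at which 50% have relapsed.

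**Second reading of the zero rule.** The protocol equates not tapering off with not reaching sustained remission, and its definition of sustained remission runs to month 12. Taken literally, patients who taper off but relapse before month 12 are also zeros. At the design rate 0.25 × 105 = 26.25 patients are non-zero, so 105 − 26.25 = 78.75, about 79, are zeros and the median is 0. The multiplication above does not apply on this reading. The 52-patient threshold still does, because month-12 responders are a subset of Step 3 patients.

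**Illustration in weeks (first reading).** Assume a Step 3 median of m = 26 weeks and Weibull relapse with shape k. The all-patient median is m(1 + log2 p)^(1/k), for 63, 74 and 84 at Step 3 respectively:

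- k = 0.7 (early relapse): 3.9, 9.5, 14.9 weeks
- k = 1 (exponential): 6.8, 12.9, 17.6 weeks
- k = 1.5 (late relapse): 10.7, 16.3, 20.1 weeks

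The results scale with m. At week 26 the Step 3 curve reads 50% and the all-patient curve 0.5p, that is 30%, 35% and 40%.

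**Borrowed rules.** Item 1c counts to relapse and includes Step 3 patients who are not month-12 responders, but the event it borrows is worded as relapse after month-12 response. The dated censoring rules name only month-12 responders. A Step 3 patient who leaves before month 12, or who had new rescue after day 14 and later completed Steps 1 to 3, can be free of relapse without being one. The protocol's censoring sentence suggests that death is not censored, while the SAP censors at death. These mismatches cannot be sized because the documents give no counts.

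**The case against.** The strongest reply is that nothing is hidden. SAP 2.7.2 itself calls the population Step 3 patients and notes that month-12 responders are a subset. That stands. A reader might infer that the SAP presents a conditional median as an all-patient one, but only SAP Table 1-1 keeps the all-patient wording. The fault is an unannounced change and an uncorrected table.

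A reader might also infer that the population was narrowed once results were known. The documents do not show this. The dated update of 2.7.2 preceded the final lock, which is the lock that matters for a month-24 endpoint, although month-12 data had been reported. Nor do they show which SAP version brought in Step 3.

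It is fair to say that FAS information survives: the primary endpoint, the share able to discontinue after tapering (SAP 2.5.4), and the proportions in response at months 15, 18, 21 and 24 (item 2). None of these gives the planned all-patient duration curve or median.

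The event and censoring mismatches are mostly loose drafting. Item 1c is also to be summarised by month-12 status, so relapses before month 12 must be meant to count, and the discontinuation date in 1b carries over naturally to early leavers. The death wording affects 1b equally. These are clarifications.

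Finally, an all-patient median of 0 says little by itself. True, but the protocol chose that rule, and a departure from it should be stated.

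**Conclusion.** The point holds. SAP 2.7.2 contradicts the protocol and the SAP's own Table 1-1 on the population for 1c, omits the zero rule, and does not declare either departure. The direction is certain on a common clock. The size is not, because the Step 3 share is unknown: the all-patient median is 0 at 52 or fewer of 105. Above that, the tabulated percentages need only the first reading of the zero rule and the assumed shares; the week values also need the assumed median and shape. On the second reading the median is 0 at the design rate.

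This should be corrected, but it is limited in reach. Item 1c is descriptive, there is no key secondary objective, and the primary test does not depend on it.

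**What to change.** - Run 1c on the FAS with the protocol's zero rule, and state whether zero means not reaching Step 3 or not reaching sustained remission at month 12.
- Because the median may be 0, also report Kaplan-Meier estimates at fixed weeks after last dose, for example 12, 26 and 52.
- Keep the Step 3 curve as a labelled supplement.
- Name the Step 3 restriction and the dropped zero rule explicitly in SAP section 4.
- As clarifications, define the 1c event as any relapse after the index last dose, before or after month 12. Extend the dated censoring rules to Step 3 patients who are not month-12 responders, and reconcile the handling of death with Protocol 12.5.1.

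The cost is SAP wording and a few lines of code, with no new data. The headline median cannot become longer and may be 0.

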Patients who relapse (< 30×10 ⁹ /L) during eltrombopag tapering off stage	Use previous dose level (i.e. one dose level higher)
Patients who relapse (< 30×10 ⁹ /L) after eltrombopag discontinuation	Re-initiate treatment with starting dose 50 mg/day (25 mg/day for Asian patients)

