2.7 Analysis of secondary efficacy objective(s)

For all efficacy and PRO analyses, the FAS will be used. For all safety analyses the safety set will be used.

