Number (%) of patients who reach platelet count $\geq 50 \times 10^9 / \text{L}$ at least once within the first month (month 1) without bleeding events and no rescue therapy will be provided.

4. To assess the ability of eltrombopag to induce a **recovery response**, in case of loss of response after tapering of eltrombopag

Number (%) of patients with at least one platelet count $\geq 30 \times 10^9 / \text{L}$ after eltrombopag is re-introduced, in case of loss of response ($< 30 \times 10^9 / \text{L}$ and/or bleeding event) without bleeding events and no rescue therapy will be provided.

5. To quantify the **platelet count** from baseline to 3, 6, 9, 12, 15, 18, 21, 24 months

Absolute and relative change in platelet count from baseline to 3, 6, 9, 12, 15, 18, 21, 24 months and EOT will be provided for all scheduled visits. Box plots for absolute and/or relative change in platelet counts from baseline to different time points will also be provided. Additionally, platelet counts ranges ($\geq 30 \times 10^9 / \text{L}$, $\geq 50 \times 10^9 / \text{L}$, $\geq 70 \times 10^9 / \text{L}$ and $\geq 100 \times 10^9 / \text{L}$) will be provided only for patients who reach sustained response off treatment at month 12.

6. To assess the ability of eltrombopag to maintain platelet count $\geq 30 \times 10^9/L$ within 12 months and every 3 months until month 24

Number (%) of patients who maintain a platelet count $\geq 30 \times 10^9/L$ from the first time of reaching that level to month 3, 6, 9, 12, 15, 18, 21, 24 and EOT, without bleeding events and no rescue therapy will be provided.

7. To evaluate patient reported outcomes using measures for Health-Related Quality of Life with the FACIT-Fatigue, **FACT-Th6** and **SF-36v2** questionnaires.

Change in each domain score and total score of PRO parameters: FACIT-Fatigue, FACT-Th6 and SF-36v2 questionnaires from baseline to 3, 6, 9, 12, 15, 18, 21, 24 months and EOT will be provided by SRoT_M12 status. In addition, summary statistics for the two main summary scores, the PCS and the MCS for SF36 v2 as per sustained response off treatment status (sustained response off treatment versus no sustained response off treatment) will also be provided. Listings will be provided.

Scoring for SF-36v2 will be provided by an external vendor.

8. To explore the overall impact of side effects of treatment via the **GP5** at baseline, 12 months and EOT.

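### The SAP narrows the recovery-response objective without declaring it, and leaves the denominator, the event-free window and the handling of bleeding-only losses undefined

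*SAP*

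**What the plan says.** **Objective.** The protocol gives the recovery-response objective in its summary, in Table 2-1 and in section 12.5.1. Table 2-1 has "in case of loss of response during or after tapering of eltrombopag until month 24", and section 12.5.1 has "in case of loss of response during or after tapering of eltrombopag". SAP 2.7.2 item 4 has "in case of loss of response after tapering of eltrombopag".

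**Endpoint.** Both documents count patients with at least one platelet count of 30 × 10⁹/L or more "after eltrombopag is re-introduced, in case of loss of response". Loss is a count below 30 × 10⁹/L, a bleeding event, or both. The sentence closes with "and/or bleeding event) without bleeding events and no rescue therapy will be provided". Protocol 12.5.1 uses the same words.

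**Time limits.** SAP Table 1-1 adds "without bleeding and no rescue therapy by month 12 and 24". SAP 2.7.2 item 4 does not repeat the limits.

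**Analysis set.** SAP 2.7 states: "For all efficacy and PRO analyses, the FAS will be used". SAP 2.2 defines the FAS as everyone who took at least one dose. Item 4 names no subset.

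**Management of a loss.** Protocol Table 6-1 has one row for relapse "during eltrombopag tapering off stage", where the patient goes back one dose level, and another for relapse after discontinuation, where treatment is started again.

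**The concern.** This endpoint is meant to show how often going back to eltrombopag restores response after a taper has failed. Three things stand in the way.

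- **Who is counted.** Patients who lose response during the taper are part of the protocol's target group. The SAP objective leaves them out without saying so.
- **What counts as recovery.** A patient who bled at a count of 30 × 10⁹/L or more already meets the platelet criterion at the moment of loss.
- **What the percentage is out of.** Only patients who lost response and went back to eltrombopag can recover. With the FAS as denominator, the result mainly reflects how many patients lost response.

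The same data could therefore give very different percentages, depending on programming choices that the SAP does not record.

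**Working it through.** The documents give no expected rate or sample size for this endpoint, so there is no planned figure to reproduce. The first two steps compare text. The last two are illustrations with assumed counts.

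**1. Is the narrowing declared?** SAP section 4 lists changes to protocol-specified analyses. Two entries reach endpoint 4: the relaxed rule on steroids after day 14, which applies to all efficacy endpoints, and the rule that bleeding counts only from day 8, which names endpoints 3, 4 and 6. The entry for section 2.7.2 says only that the description was updated and that event and censoring rules were added. None mentions removing losses during tapering.

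**2. Does the endpoint sentence settle the scope?** No. It does not mention tapering. It requires a count after eltrombopag is re-introduced. Under Table 6-1, a patient who relapses in mid-taper goes back one dose level, so the drug was never stopped. Whether that is a re-introduction is not stated. The tension is already present in the protocol, between its objective and its endpoint.

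**3. Denominator.** Input: 105 enrolled (SAP section 1), taken as the FAS size on the assumption that all were dosed. Assumed: L patients lose response and return to eltrombopag, and 80% of them recover.

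| L | Recovered | Share of FAS | Share of those at risk | Highest possible share of FAS |
|---|---|---|---|---|
| 15 | 12 | 12/105 = 11.4% | 12/15 = 80% | 15/105 = 14.3% |
| 30 | 24 | 24/105 = 22.9% | 24/30 = 80% | 30/105 = 28.6% |
| 60 | 48 | 48/105 = 45.7% | 48/60 = 80% | 60/105 = 57.1% |

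Over the FAS, the percentage cannot exceed L/105 even if every patient with a loss recovers.

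**4. Bleeding-only losses.** Let b be the share of losses that are bleeding-only, q_b the share of those scored as recovered, and q_p the share of platelet losses that recover. Rate among losses = b·q_b + (1 − b)·q_p. Take b = 0.4 and q_p from 0.5 to 0.7, all assumed.

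- If the window starts at re-introduction and q_b = 0.95: 0.38 + 0.30 = 68% up to 0.38 + 0.42 = 80%.
- With the same window and q_b = 0.70: 0.28 + 0.30 = 58% up to 0.28 + 0.42 = 70%.
- If the window includes the triggering bleed, q_b = 0: 0 + 0.30 = 30% up to 0 + 0.42 = 42%.

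The undefined window can thus move the result in either direction.

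**The case against.** Three stronger readings are tempting. The documents do not support any of them as stated.

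**That the SAP removes losses during tapering from the count.** The changed word is in the objective line. The sentence that defines the count is the same in both documents, and its re-introduction condition may already leave out many such losses under the protocol. This stands. Restoring the objective wording alone would not settle who is counted, but the undeclared mismatch remains.

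**That bleeding-only losses are scored as recovered almost automatically.** The patient must also be free of bleeding and rescue therapy, and bleeding is the very criterion that failed. If the triggering bleed falls inside the window, such a patient could never recover. The rule also comes from the protocol, and Table 6-1 ties renewed treatment to counts below 30 × 10⁹/L, so the number of bleeding-only losses that would qualify is unknown. What remains is that the platelet criterion is uninformative for these patients and the window is undefined.

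**That the SAP prescribes division by the FAS.** An analysis set is not a denominator. Under the same FAS sentence, items 1a to 1c and part of item 5 use subsets. The wording on loss of response can be read as conditional, and the table shells and programming specifications are separate documents not available here. This stands too: the FAS is the default reading, not an explicit rule. Yet those other items name their subsets and item 4 does not, so the gap is real.

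Finally, the endpoint is secondary and descriptive, and SAP 2.6 names no key secondary objective. That limits the weight of the point but does not remove it.

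**Conclusion.** The concern holds as a problem of specification. The SAP objective is narrower than the protocol's, and the change is undeclared. The endpoint sentence does not clearly cover losses during tapering as Table 6-1 handles them, so the objective, the endpoint and Table 6-1 must be reconciled. The platelet criterion cannot show recovery after a bleed at a count of 30 × 10⁹/L or more, and the event-free window is open to opposite readings. The denominator is unstated and defaults to the FAS.

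The size depends on the number of losses, which the documents do not give. At an assumed 80% recovery, the default reading reports 11.4% to 45.7% for 15 to 60 losses. These figures also assume that all 105 enrolled patients were dosed. The correction should be made, but it concerns one descriptive table.

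**What to change.** 1. In SAP 2.7.2 item 4, restore the protocol scope and state that the endpoint covers losses during tapering as well as after discontinuation. Otherwise, declare and justify the narrowing in section 4.
2. State the denominator: patients with a loss of response who resumed eltrombopag or stepped back up in dose.
3. Start the bleeding- and rescue-free window at that point, and carry over the month 12 and month 24 limits from Table 1-1.
4. Keep the protocol-defined endpoint, but report losses with a count below 30 × 10⁹/L and bleeding-only losses in separate rows.

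Redefining recovery to exclude bleeding-only losses is not needed. It would replace a protocol endpoint after the primary CSR was final.

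The cost is SAP wording and one re-cut descriptive table. Because the primary CSR was already final at this SAP version, the table should be labelled as specified after it.
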